## 9.3 Treatments

Study drug administration and concomitant medication data will be listed and summarized using the Safety set. The duration of exposure, the number of patients randomized who completed the treatment period, and who discontinued from study medication will be summarized.

Medications started and stopped prior to study drug and taken concomitantly, will be summarized by treatment group in separate tables in the Safety Set.

Concomitant therapies will be recorded, listed and summarized separately for asthma related medications / non-drug therapies and other medications. Concomitant asthma related medications will be summarized by pharmacological (ATC) class and preferred term.

Concomitant medications not related to asthma will be summarized by ATC class. More than one ATC class per medication is possible and the medication will be reported under all applicable classes.

SABA usage (number of puffs) during the Screening epoch will be summarized.

Patients taking prohibited concomitant medications will be noted in the summary of protocol deviations.

Treatment compliance with study medication over the study period will be summarized.

## 9.4 Analysis of the primary variable(s)

### 9.4.1 Variable(s)

The primary endpoint is change from baseline in pre-dose trough FEV1 (mL) after 2 weeks of treatment. The pre-dose trough FEV1 (mL) is defined as the mean of the two FEV1 (mL), values measured at -45 min and -15 min pre-dose.

### 9.4.2 Statistical model, hypothesis, and method of analysis

The dose selection will be based on the totality of clinical, physiological and PK data in pediatric patients  $\geq$  6 years and  $<$  12 years years old. Summary statistics (n, mean, 25th percentile, median, 75th percentile, standard deviation, minimum and maximum) by treatment

group will be provided for change from baseline in pre-dose trough FEV1 as well as pre-dose trough FEV1 after 2 weeks of treatment. Inferential testing statistics will not be performed since the sample size is small and power is limited.

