**Figure 3-1 Study design**

### 3.2 Rationale for study design

This study is a randomized, double-blind, parallel-group study, with a 2-week treatment duration to assess 2 different doses of indacaterol acetate. The primary endpoint, trough FEV1, will be evaluated as change from baseline (randomization) after 2 weeks. This is considered an adequate duration to demonstrate improvements in the primary endpoint of lung function based on the known pharmacodynamic properties of indacaterol.

In order to preserve the integrity of the study, a randomized, double-blind study design is used. This design enables the study treatments to be given for an appropriate and practical length of time to assess the efficacy and safety of the treatments. The study design does not include a placebo control, as this would not be considered ethical in this population of pediatric asthma patients with GINA  $\geq$  Steps 2 and 3 (GINA 2015).

The primary objective of this trial is to evaluate the efficacy of 2 doses of indacaterol in patients with persistent asthma in terms of lung function (measured by pre-dose FEV1). Other efficacy endpoints include peak expiratory flow, rescue medication, and FEV1 at 30 minutes and 1 hour post-dose.

Additional secondary endpoints include the evaluation of the systemic exposure to indacaterol in plasma according to a sparse PK sampling ( $\leq$  2 hours pre-dose, and 15 minutes and 1 hour post-dose). This will allow comparison of the systemic exposure to indacaterol after single dose (Day 1) and at steady state (Day 14) observed in these pediatric patients with that collected in adult healthy subjects or patients (historical data). Safety is also evaluated.

The lung function data combined with systemic exposure will be used to identify an appropriate dose of indacaterol which will be carried forward to the Phase 3 pediatric trials. The primary endpoint, change in baseline of pre-dose trough FEV1, will be evaluated descriptively as a function of change from baseline between the two indacaterol doses. Taken together with systemic exposure for each dose, which will be compared with historical PK data collected in adults, an appropriate dose will be selected.

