### **3.4 Rationale for choice of comparator**

It was considered appropriate to explore two doses of indacaterol acetate, 75 µg o.d. and 150 µg o.d. in 6-11-year-olds and to compare the systemic exposure obtained in this trial with that obtained in adults (historical data). Relative differences in lung function between 2 doses will be evaluated descriptively.

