## **5.3 Treatment assignment and randomization**

At Visit 201, all eligible patients will be randomized via Interactive Response Technology (IRT) to one of the treatment arms above. The investigator or his/her delegate will contact the IRT after confirming that the patient fulfills all the inclusion/exclusion criteria. The IRT will assign a randomization number to the patient, which will be used to link the patient to a treatment arm and will specify a unique medication number for the first package of study drug to be dispensed to the patient. The randomization number will not be communicated to the caller.

The randomization numbers will be generated using the following procedure to ensure that treatment assignment is unbiased and concealed from patients/subjects and investigator staff. A patient randomization list will be produced by the IRT provider using a validated system that automates the random assignment of patient numbers to randomization numbers. These randomization numbers are linked to the different treatment arms, which in turn are linked to medication numbers. A separate medication list will be produced by or under the responsibility of Novartis Drug Supply Management using a validated system that automates the random assignment of medication numbers to packs containing the investigational drug(s). Randomization will be stratified by region.

The randomization scheme for patients will be reviewed and approved by a member of the COAR Randomization Group.

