## **9.7 Sample size calculation**

The sample size of 72 patients evaluable for the primary endpoint in the study is based on pragmatic considerations and per agreement with EU Pediatric Committee (PDCO), not based on statistical considerations. It is assumed that approximately 10% of patients will not complete the trial so that 80 patients need to be randomized to ensure 72 patients will be evaluable for the primary endpoint.

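### The primary analysis lists only unadjusted per-arm summaries: no 150 minus 75 µg difference in trough FEV1 change with a confidence interval, and no use of baseline FEV1 or region

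*Protocol*

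**What the plan says.** Section 9.4.1 sets the variable: "The primary endpoint is change from baseline in pre-dose trough" FEV1 after two weeks, where trough is the mean of the readings 45 and 15 minutes before dosing. Section 9.4.2 then gives the method: n, mean, quartiles, median, SD, minimum and maximum in each treatment group, for trough FEV1 and for its change. It closes with "Inferential testing statistics will not be performed since the sample size is small and power is limited". The synopsis repeats this, and section 9.4.4 adds the same kind of summaries in the per-protocol set. The analysis section names no between-arm difference, interval, model or covariate for this endpoint.

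Other sections give the dose comparison a purpose. Section 3.2 says the primary endpoint "will be evaluated descriptively as a function of change from baseline between the two indacaterol doses". Section 3.4 says "Relative differences in lung function between 2 doses will be evaluated descriptively". Section 9.4.2 itself says "The dose selection will be based on the totality of clinical, physiological and PK data". On allocation, section 5.3 states "Randomization will be stratified by region". Section 9.7 plans 80 randomised patients "to ensure 72 patients will be evaluable for the primary endpoint".

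**The concern.** The trial has no placebo arm, so 150 versus 75 µg is its only randomised comparison. A change from baseline within one arm mixes drug effect with regression to the mean and with any change in adherence to the background inhaled steroid. Only the between-dose difference is protected by randomisation, and the list of planned outputs leaves it out.

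The stated reason does not support the omission. Limited power argues against a hypothesis test, because a non-significant result would say little. It does not argue against an estimate with an interval, which is how a small study shows what it cannot distinguish.

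Baseline trough FEV1 is subtracted but not used as a covariate, so a chance imbalance in baseline carries into the comparison of mean changes to the extent that change depends on baseline. Region was important enough to stratify on, yet it has no role in the analysis. At stake is a Phase III paediatric dose choice in which two arm means may be read side by side without the width of the uncertainty between them being displayed.

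**Working it through.** **The plan's own figure.** Section 9.7 allows for about 10% non-completion: 72 / (1 − 0.10) = 80 randomised. This reproduces. At the 1:1 ratio of section 5.2, the 72 evaluable patients are 36 per arm. There is no power calculation to reproduce, because section 9.7 says the number is pragmatic.

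**Assumptions.** The protocol gives no SD and no correlation. I assume an SD of change of 200 to 350 mL, a correlation r between baseline and Week 2 of 0.6 to 0.9, equal variance at both visits, and 2 to 4 regions (needed only for degrees of freedom).

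**Unadjusted difference.** SE = SD × √(2/36); half-width of the 95% interval = t(0.975, 70 df) × SE, with t = 1.994.

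- SD 200 mL: SE = 47.1 mL; half-width = 94.0 mL.
- SD 350 mL: SE = 82.5 mL; half-width = 164.5 mL.

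**Adjusted for baseline.** With equal variance σ² at each visit, the change has variance 2σ²(1 − r) and the ANCOVA residual has variance σ²(1 − r²). The ratio of standard errors is therefore √((1 + r)/2).

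- r = 0.9: ratio = √0.95 = 0.975, a reduction of 2.5%.
- r = 0.6: ratio = √0.80 = 0.894, a reduction of 10.6%.

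The adjusted half-width uses t on 66 to 68 df (1.997 to 1.995):

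| SD of change | Unadjusted | r = 0.9 | r = 0.6 |
|---|---|---|---|
| 200 mL | ±94 mL | ±92 mL | ±84 mL |
| 350 mL | ±165 mL | about ±160 mL | ±147 mL |

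No gain in precision from region is assumed.

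**How sensitive the gain is.** One can instead assume the correlation c between change and baseline (in absolute value) and multiply the SE by √(1 − c²). At SD 300 mL the unadjusted half-width is ±141 mL. With baseline adjustment alone it becomes ±135, ±122 and ±101 mL for c = 0.3, 0.5 and 0.7. Under equal variances c² = (1 − r)/2, so r = 1 − 2c², and these values correspond to r = 0.82, 0.50 and 0.02. The large gain at c = 0.7 therefore needs almost no correlation between the two visits. The range of 2.5 to 10.6% is the more cautious one.

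**What the interval would show.** Suppose, for illustration only, that one dose is truly 50 mL better. The chance that the other arm has the larger observed mean is Φ(−50/SE): 0.14 at SD 200 mL and 0.27 at SD 350 mL.

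**The case against.** The best defence is that the protocol is descriptive throughout and says so openly. The primary objective in section 2.1 is to evaluate each dose on change from baseline, which per-arm summaries do. Sections 3.2 and 3.4 promise a descriptive look at the doses, not an interval or a model, and the difference is one subtraction away. The sample size was agreed with the EU Pediatric Committee, the dose choice rests on PK and symptoms as well, and no FEV1 threshold is set that an interval could cross. A SAP, not available here, may add the display.

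Much of this stands. There is no arithmetic error, no invalid test and no flat contradiction. A reader can compute an unadjusted interval from the planned n, mean and SD. The gain from adjustment is modest and depends on assumed correlations, and none is claimed from region. It cannot be shown that the interval would change the dose chosen.

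It does not remove the point. An adjusted difference cannot be recovered from arm summaries. Section 9.4.2 carries the primary method and defers nothing, whereas section 9.1 expressly leaves the per-protocol exclusion rules to the SAP. Its closing sentence could even be read as barring an interval. The agreement cited in section 9.7 concerns the number of patients, which the fix leaves alone.

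**Conclusion.** The concern holds, as an improvement that should be made and not as a fatal flaw. The protocol says the doses will be compared on change in trough FEV1, but plans no statistic for that comparison, and its reason for not testing does not cover leaving out an estimate.

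With 36 evaluable per arm and an assumed SD of change of 200 to 350 mL, the missing interval would be about ±94 to ±165 mL wide on each side. Baseline adjustment would narrow this to about ±84 to ±92 mL at SD 200 mL, or ±147 to ±160 mL at SD 350 mL, for r between 0.6 and 0.9 with equal variances. The main gain is a visible statement of uncertainty. The smaller gains are some precision and protection against chance baseline imbalance. All SDs and correlations are assumptions, so confidence in the size is moderate. That the output is absent from the planned analysis is clear from the text.

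**What to change.** In section 9.4.2 and the synopsis, keep the statement that no hypothesis test will be done and keep all the per-arm raw summaries. Add, for the Full Analysis Set, an ANCOVA of change from baseline in trough FEV1 with dose, baseline trough FEV1 and region as terms. Report the adjusted mean change in each arm and the adjusted 150 minus 75 µg difference, each with a 95% confidence interval. State that the intervals are for estimation and carry no test or claim of superiority.

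The cost is one model, one table and a wording change in two places. Baseline FEV1 and region are already collected, and no patients or visits are added.

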#### **9.4.3 Handling of missing values/censoring/discontinuations**

If any of the -45 min and -15 min values contributing to the pre-dose trough FEV1 are collected within 7 days of systemic corticosteroid use, 6 hours of rescue medication, or actual measurement times are outside the 22 - 25 hour from last dose of the previous day (Day 13) then the individual FEV1 value will be set to missing.

If one of the two values is missing (or set to missing) then the remaining non-missing value will be taken as pre-dose trough FEV1. If both values are missing, or if the patient withdrew from the study, regardless of the reason for discontinuation, then pre-dose trough FEV1 will be regarded as missing in which case the missing value(s) of the patient at the particular visit(s) would not contribute to the summary statistics.

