#### **5.5.4 Instructions for prescribing and taking study treatment**

Patients will be provided with medication as described in [Section 5.1](#).

Study medication prescribed and dispensed to the patient and all dose changes during the study must be recorded on the Dosage Administration Record CRF (e-CRF).

At Visit 1 all patients (and parent/legal guardian) will be instructed how to use the inhalers to administer rescue salbutamol/albuterol and the fluticasone propionate correctly. Patients and parent/legal guardian will be trained to use the peak flow meter and e-Diary as well.

Beginning at Visit 101, patients will be fully trained in the correct use of the Concept1 inhaler device used to administer study medication. Patients/parents who are unable to use the device correctly will not be eligible to enter the treatment epoch. Additional training devices will be supplied for demonstration purposes. At clinic visits the investigator should check the patient's use of the inhalational device to ensure that the child is using the device correctly. Additional device training may be provided if required.

At randomization, the patient will take a single inhalation, from the Concept1 device, while at the site.

**Patients, along with their parent/ legal guardian will be instructed to take one inhalation from the Concept1 device once daily, at approximately the same time each day during the two-week timeframe. Dosing should be done in the morning, following the patient's morning dose of fluticasone propionate.** Parents/legal guardian should be instructed to rinse the child's mouth after inhalation of study drug. Water used for mouth rinsing should be

spat out and should NOT be swallowed. Patients should take their 2nd dose of fluticasone propionate in the evenings.

**The time of study medication taken on morning of Day 13 (or one day prior to Day 14/Visit 299/End of Treatment) should be recorded by the parent and brought to the clinic at Visit 299. The child should not take study medication at home on the morning of Visit 299 (end of treatment visit). Study medication will be taken at the site on this day, under staff supervision.**

All kits of study treatment assigned by the IRT will be recorded/databased in the IRT. All used and unused study medication/packaging must be returned at each study visit and/or at the time of discontinuation.

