Visit	1	101	199	201	299	301 
Day Note: V199 and 201 will occur on the same day if the patient is randomized.	Up to 30 days prior to Visit 101	-14	1	1	14	44
Record time of study drug taken one day prior (Day 13) to Visit 299/Day 14					X**	
Collect unused study medication					S**	
Record interruption/ changes in study drug administration to assess compliance				X	X**	
AE recording		X	X	X	X**	X
SAE recording	X	X	X	X	X**	X
Review and record surgeries and procedures		X	X	X	X**	X
Study disposition (Screening)	X					
Study disposition (Run-in)			X			
Study disposition (End of Treatment)					X**	
Study disposition (Follow-up)						X
Safety Lab assessments 		X	X		X**	

Epoch	Screening*	Run-in		Treatment		Follow-up
					End of study treatment/ Early termination**	
Visit	1	101	199	201	299	301 
Day Note: V199 and 201 will occur on the same day if the patient is randomized.	Up to 30 days prior to Visit 101	-14	1	1	14	44
(hematology, chemistry, urine dipstick)						
PK sampling 			X	X	X**	
ACQ-IA 		X	X		X**	
Telephone parent/ legal guardian in advance of study visit, with reminder to not take rescue medication within 6 hours of study visit, and bring in all study medication and e-Diary		S	S	S	S	

\*Screening Visit 1 and Run-in Visit 101 can occur on the same day if patient did not take any salbutamol/albuterol within 6 hours of the study visit.

\*\*These assessments should be conducted for patients who discontinue.

S These assessments are source documentation only and will not be entered into the CRF.

X Assessment to be reported in the clinical database.

For females of child-bearing potential only.

Labs and urine dipstick are done pre-dose.

Details of timed assessments are provided in [Table 6-2](#) and [6-3](#).

Device training at Visit 1 is for e-diary/peak flow meter, salbutamol/albuterol and fluticasone propionate inhaler. Device training at Visits 101 and 199 is for Concept1.

The ACQ-IA is completed at the clinic, before any other assessment.

Information about any AEs/ SAEs occurring within 30 days of the patients' last study treatment will be obtained by a telephone call 30 days after the patient's last dose of study drug for completed patients. For patients who withdraw early, please refer to discontinuation of study treatment and premature patient withdrawal Section.

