## **6.3 Treatment exposure and compliance**

The time of study treatment dosing, at Visit 201 and 299/End of treatment, will be collected on the e-CRF as well as any dosing interruptions. For assessments where spirometry is performed, the time of dosing is to be taken from the spirometer.

Study treatment compliance should be assessed by the investigator and/or center personnel at all visits. Where necessary, the Investigator will discuss compliance/documentation issues with the patient's parent/legal guardian. The Investigator or designee will collect, from the patient's parent/legal guardian, the used/unused investigational medication and packaging (unused capsules/blister strips SDDPIs) at Visits 299/End of Treatment/ Early Treatment Discontinuation. Study treatment compliance will be assessed from the capsule count from previously dispensed blister strips for the Concept1®.

The number of puffs of rescue medication (salbutamol/albuterol) between study visits will be recorded by the patient's parent/ legal guardian in the e-Diary.

Fluticasone use should be assessed by the investigator and/or center personnel at all visits. The investigator or designee should ask the patient and parent about their daily fluticasone use and should document this in the patient's source document as well as in the eCRF.

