### **6.4.1 Spirometry assessments**

The following spirometry assessments will be made:

- Forced expiratory volume in 1 second (FEV1)
- Forced Vital Capacity (FVC)
- Spirometric assessments will be measured at Visits 199, 201 and 299/EOT as indicated in [Table 6-1](#) through [Table 6-3](#).
- Pre-dose FEV1 is defined as the mean of the two FEV1 values measures at -45 min and -15 min prior to morning dose.

Please refer to the Spirometry Guidance in [Appendix 3](#) and [Table 6-2](#) and [Table 6-3](#) for full details on scheduling and performing spirometry.

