#### **7.4 Reporting of study treatment errors including misuse/abuse**

Medication errors are unintentional errors in the prescribing, dispensing, administration or monitoring of a medicine while under the control of a healthcare professional, patient or consumer (EMA definition).

Misuse refers to situations where the medicinal product is intentionally and inappropriately used not in accordance with the protocol.

Abuse corresponds to the persistent or sporadic, intentional excessive use of a medicinal product, which is accompanied by harmful physical or psychological effects.

Study treatment errors and uses outside of what is foreseen in the protocol will be collected in the DAR (dose administration record) e-CRF irrespective of whether or not associated with an AE/SAE and reported to Safety only if associated with an SAE. Misuse or abuse will be collected and reported in the safety database irrespective of it being associated with an AE/SAE.

Treatment error type	Document in Dose Administration (DAR) e-CRF (Yes/No)	Document in AE e-CRF	Complete SAE form
Unintentional study treatment error	Yes	Only if associated with an AE	Only if associated with an SAE
Misuse/Abuse	Yes	Yes,	Yes, even if not associated with a SAE

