#### **9.1 Analysis sets**

The following analysis sets are defined for data analysis.

- The Randomized Set (RAN) will consist of all patients who were assigned a randomization number; regardless they actually received study medication. Several tables will summarize all screened subjects (e.g. “Screening Phase subject disposition, All screened subjects” and “Analysis sets by treatment, All subjects”). In consistency with the master analysis plan (MAP), there will not be a definition of a screened set.
- The Full Analysis Set (FAS) will consist of all patients in the RAN who received at least one dose of study medication. Following the intent-to-treat principle, patients in the FAS will be analyzed according to the treatment they were randomized to in the assigned treatment sequence. The FAS will be used in the analysis of all efficacy variables.
- The Per Protocol Set (PPS) will include all patients in the FAS who did not have any major protocol deviations. Rules for exclusion of subjects from the PPS will be defined in the Statistical Analysis Plan (SAP) prior to database lock and the un-blinding of the study. Patients in the PPS will be analyzed according to the treatment they actually received. The PPS will be used for supportive analysis of the primary analysis.
- The Safety Set will consist of all patients who received at least one dose of study medication. Patients in the Safety Set will be analyzed according to treatment received. The Safety Set will be used in the analysis of all safety variables.

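### Section 9.4.3 times the Visit 299 trough FEV1 from the Day 13 dose rather than the most recent dose, so readings after an early, forbidden home dose that morning can stay in the primary summary

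*Protocol*

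**What the plan says.** The primary endpoint (section 9.4.1) is the change from baseline in pre-dose trough FEV1 after 2 weeks, the trough being the mean of two readings. Section 6.4.1 defines these as "values measures at -45 min and -15 min prior to morning dose".

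Section 9.4.3 names three grounds for setting one of these readings to missing: systemic corticosteroid within 7 days, rescue medication within 6 h, or "actual measurement times are outside the 22 - 25 hour from last dose of the previous day (Day 13"). If one reading is lost, "then the remaining non-missing value will be taken as pre-dose trough" FEV1. If both are lost, the child has no trough.

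On dosing, section 5.5.4 says: "The child should not take study medication at home on the morning of Visit 299 (end of treatment visit"). Section 3.1 gives the same instruction. Section 3.1 also requires the visit to be rescheduled if the Day 13 dose was missed or if rescue medication was taken within 6 h. For a morning fluticasone dose taken at home, it says to document the fact and carry on. Neither section says what to do with the visit or the readings if study drug was taken at home that morning.

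On recording, section 6.3 says that for spirometry assessments "the time of dosing is to be taken from the spirometer". Table 6-1 has a row databased at Visit 299: "Record interruption/ changes in study drug administration to assess compliance". Section 7.4 adds: "Study treatment errors and uses outside of what is foreseen in the protocol will be collected in the DAR" e-CRF. On the analysis set, section 9.1 says: "The FAS will be used in the analysis of all efficacy variables".

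**The concern.** A trough window should confirm that a reading was taken about a day after the last active dose. This one confirms only that it was taken about a day after the Day 13 dose. In ordinary use the two are the same. They part when a child who has taken study drug at home every morning does so again on the visit morning. A reading an hour or two after that dose reflects fresh bronchodilation, yet it can pass the window.

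The result is inconsistent within a single rule. A reading within 6 h of a short-acting rescue bronchodilator is removed, while a reading 1-2 h after the long-acting bronchodilator under test may be kept. At stake is the by-arm summary of change in trough FEV1, one of the inputs to dose selection. There is no placebo arm, so each arm's change from baseline has no concurrent reference against which such an error would show.

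**Working it through.** **The plan's own figure.** Section 9.7 randomises 80 so that 72 are evaluable with about 10% loss: 72 / (1 - 0.10) = 80, which reproduces. At 1:1 this is 72 / 2 = 36 evaluable children per arm.

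**Inputs.** The 22-25 h window is from section 9.4.3. The readings at -45 and -15 min, 0.5 h apart, are from sections 6.4.1 and 9.4.1. The lag from home dose to first reading is not in the protocol. Table 6-3 starts the Visit 299 pre-dose work up to about 2 h before dosing and puts the first reading 0.75 h before dosing, so on-site work alone can take 2 - 0.75 = 1.25 h. I use lags of 1.25 h (no travel) and 2 h (0.75 h of travel) as a range.

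**Formula.** Let g be the hours from the Day 13 dose to the home dose and L the lag in hours. The readings fall g + L and g + L + 0.5 hours after the Day 13 dose.

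- Both are kept if 22 ≤ g + L ≤ 24.5.
- At least one is kept if 21.5 ≤ g + L ≤ 25.
- A home dose at g hours is 24 - g hours earlier by the clock than on Day 13.

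| Lag L | Both kept | At least one kept | Earlier than Day 13, one kept | Earlier than Day 13, both kept |
|---|---|---|---|---|
| 1.25 h | g = 20.75 to 23.25 | g = 20.25 to 23.75 | 0.25 h (15 min) | 0.75 h (45 min) |
| 2 h | g = 20 to 22.5 | g = 19.5 to 23 | 1 h | 1.5 h |

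**Kept example.** Day 13 dose at 08:00, home dose at 07:00 on Day 14, readings at 08:15 and 08:45. From Day 13 these are 24.25 and 24.75 h, so both are kept. From the home dose they are 1.25 and 1.75 h.

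**Caught example.** Home dose at the usual 08:00, readings at 09:15 and 09:45. From Day 13 these are 25.25 and 25.75 h, so both are set to missing.

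**Limit of the 25 h bound.** The latest reading that can be kept is 25 - g hours after the home dose: 1.0 h if g = 24, 1.5 h if g = 23.5, 2.0 h if g = 23. If the bound removes only the second reading, section 9.4.3 uses the first alone, and that reading is also post-dose.

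**Size.** Assume that the affected child's FEV1 is 50-200 mL above its true trough; the protocol gives no such figure. One child then moves an arm mean by 50 / 36 = 1.4 mL to 200 / 36 = 5.6 mL.

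**After the change.** Timed from the most recent dose, the readings in the kept example have intervals of 1.25 and 1.75 h. Both lie outside 22-25 h and are set to missing.

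**The case against.** The strongest reply is that the endpoint definition already excludes these readings. A child who has taken the morning dose at home has no reading before the morning dose, section 9.4.3 only screens values that contribute to a pre-dose trough, and it does not say that its grounds are exhaustive. This supports exclusion but does not secure it. Table 6-3 puts time 0 at the dose given at the visit, and section 6.3 takes the dosing time from the spirometer. If a site dose follows, the -45 and -15 min labels attach to that dose, and nothing in section 9.4.3 tells the analyst to override them.

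A second reply is that the slip is forbidden, would probably be recorded, and could be handled in the SAP. All of that may be so. But recording a deviation does not remove the value from the FAS, the PPS is only supportive, and the anchor is a rule that the protocol itself states.

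A third reply stands in full: the 15 and 45 min thresholds rest on a short lag. With 2 h, the home dose must be 1 to 1.5 h early, although parents are told to dose at about the same time each day.

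A reader might infer that every home-dosed child contributes a false trough. The documents do not support this: a home dose at the usual time or later is largely caught by the 25 h bound. A reader might also infer that the dose comparison or the dose choice is compromised. That is not supported either. Both arms have the same instructions, so some of the effect may cancel between them. The analysis is descriptive, and section 9.4.2 bases the choice on the totality of clinical, physiological and PK data.

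**Conclusion.** The point holds as a minor one. The window is anchored to the wrong dose, and the gap opens only when a forbidden home dose is also earlier than usual: by roughly 15 to 45 min at a 1.25 h lag, or 1 to 1.5 h at a 2 h lag. The likely effect is small, at about 1.4-5.6 mL on an arm mean per affected child. The timing arithmetic follows from the protocol's window once a lag is assumed. The lag and the 50-200 mL excess are assumptions, and the protocol gives no basis for how many children would be affected. The reason to act is that correction is cheap, not that the result is in danger.

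**What to change.** In section 9.4.3, replace the reference to the previous day's (Day 13) dose with: *from the most recent study-drug dose taken before the reading*. No further sentence is needed, because an interval of 1-2 h is then outside 22-25 h.

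That wording works only if the dose is known. So, on arrival at Visit 299, ask whether study drug was taken that morning. If it was, record the time, give no second dose that day, and reschedule to the next morning. The protocol already reschedules for rescue use and for a missed Day 13 dose. This saves the endpoint: the recorded home dose becomes the start of a proper trough interval. If the visit cannot be rescheduled, the trough is set to missing.

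The cost is one phrase, one question on arrival, and an occasional rescheduled visit or missing value. Each missing value is 1 / 36, about 2.8% of an arm, and the value lost was not a trough. A child who cannot be rescheduled would also have no Visit 299 post-dose measurements timed from a supervised dose.
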